**Table 1-1: Schedule of activities**

Visit frequency									
Period	Scr Period	Sampling Period							SFU a
		In-Clinic Period			Home or In-Clinic Assessments c				
Name	Scr Visit	V2 b	V3	V4 c	V5	V6	V7	V8/EW d	
Visit #	CCI								
Week									
Day									
Visit window		±0day	±0day	±0day	±0day	±0day	±0day	±0day	±5day
Procedure/activities									
12-lead ECG k	X								
Pregnancy test l	X	X						X	
Clinical laboratory tests (hematology, clinical chemistry, urinalysis) m	X	X n		X					
Blood sampling (rozanolixizumab concentration) o		X	X	X	X	X		X	
Mature breast milk collection and sampling (rozanolixizumab concentration) p		X	X	X	X	X	X	X	
Rozanolixizumab administration	CCI								
Adverse event review q	X	X	X	X	X	X	X	X	X

AESM=adverse events of special monitoring; ECG=electrocardiogram; EW=early withdrawal; Scr=Screening; SFU=Safety Follow-Up; V=Visit

a A SFU telephone call will occur on Day 57 (±5 days).

- b Study participants can be admitted to the clinic either in the early morning of Day 1 or the day before (Day -1) in the evening.
- c Study participants may be discharged beginning on Day 3 after completion of all planned assessments to be conducted at the clinic. Study participants, at their own discretion, may remain at the clinic and be discharged on a subsequent Study Day through Day 7 after completion of all planned assessments for that day's visit. After discharge, visits may be completed in the study participant's home setting in the presence of a qualified nurse. To facilitate these visits, the study participant should have access to a telephone. Alternatively, study participants may visit the clinic for assessments and blood sampling, and/or to bring into the clinic the collected breast milk.
- d Study participants who withdraw from the study during the Sampling Period will be asked to undergo the EW Visit procedures and will be encouraged to have a SFU telephone call on Day 57 ( $\pm 5$  days).
- e Individuals who do not meet the criteria for participation in this study (screen failure) may be rescreened under certain circumstances (see Section 5.4).

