#### AEs

Adverse events will be captured from the time of consent until the SFU Visit. All AEs will be coded using the Medical Dictionary for Regulatory Activities (MedDRA).

The occurrence and incidence of treatment-emergent adverse events (TEAEs) will be summarized by MedDRA system organ class and preferred term for the SS. A TEAE is defined as any AE with a start date/time on or after the dosing of study medication until 8 weeks after dosing of study medication. The occurrence and incidence of TEAEs will also be summarized by intensity and by relationship to rozanolixizumab. Adverse events leading to discontinuation and SAEs will also be summarized.

Further details on all safety analyses will be given in the SAP.

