## 1.1 Objectives and endpoints

**Table 1-1: Objectives and endpoints**

Objectives	Endpoints
Primary	

 
To assess the concentration of rozanolixizumab in mature breast milk of healthy study participants following administration of a single dose of rozanolixizumab
 
	
The primary PK endpoint is concentration of rozanolixizumab in breast milk over a 7day Sampling Period.
 
The secondary PK endpoints are:
 
 
Estimated daily infant dosage
 
Relative infant dose of rozanolixizumab from breast milk
 

Secondary	

 
To assess the safety of a single dose of rozanolixizumab administered to healthy study participants
 
	
The secondary safety endpoint is occurrence of TEAEs from Day 1 through the SFU Visit.

Exploratory/Other	

 
To determine PK parameters of rozanolixizumab in mature breast milk and plasma of healthy study participants following administration of a single dose of rozanolixizumab
 
	
The exploratory/other PK endpoints are:
 
 
<math>C_{max}</math>, <math>t_{max}</math>, <math>AUC_{(0-7d)}</math> in breast milk and plasma
 
<math>Ae_{7d}</math> and Fe in breast milk
 
Milk:plasma <math>AUC_{(0-7d)}</math> ratio
 

$Ae_{7d}$ =cumulative total amount of drug excreted in milk to Day 7;  $AUC_{(0-7d)}$ =area under the concentration-time curve from 0 to 7 days; d=day;  $C_{max}$ =maximum plasma or milk concentration; Fe=fraction of dose excreted in milk; PK=pharmacokinetic(s); SFU=Safety Follow Up; TEAE=treatment emergent adverse event;  $t_{max}$ =time to maximum plasma or milk concentration

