#### **4.1.1 Analysis time points**

##### **4.1.1.1 Study periods**

The study periods are as follows:

- Screening Period (Visit 1: Day -28 to -1)
- Sampling Period (Visits 2 to 8: Days 1 to 7)
- SFU Period (Days 8 to 57)

A study participant is considered to have completed the study if she has completed all periods of the study including the SFU period and did not discontinue the study early.

Visit 9 is a SFU telephone call which will occur on Day 57 ( $\pm 5$  days).

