#### 4.1.1.3 Relative day for listings

Relative day for an event or measurement occurring before the date of the first dose will be calculated as follows:

$$\text{Relative Day} = \text{Event/Measurement Date} - \text{Date of First Dose}$$

Relative day for an event or measurement occurring on the date of the first dose is 1.

Relative day for an event or measurement occurring on the date of the first dose will be calculated as follows:

$$\text{Relative Day} = (\text{Event/Measurement Date} - \text{Date of First Dose}) + 1$$

Relative day for an event or measurement occurring after the date of the first dose to the date of the last visit will be calculated as follows:

$$\text{Relative Day} = +(\text{Event/Measurement Date} - \text{Date of First Dose})$$

There is no relative day 0. Relative day will not be calculated for partial dates, instead relative day will be presented as '--' in the relevant participant data listing.

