### **4.3 Secondary endpoints analysis**

#### **4.3.1 Treatment-emergent adverse events**

##### **4.3.1.1 Definition of endpoint**

All adverse events (AEs) will be coded using MedDRA® version 27.1 and characterized as pretreatment and treatment emergent according to the intake of treatment. Adverse events with a start date prior to the first and only dose of treatment will be defined as pretreatment AEs. A TEAE is defined as any AE with a start date/time on or after the dosing of study medication until 8 weeks (56 days) inclusive after dosing of study medication.

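### The TEAE window closes on Day 57, while the safety endpoint and AE capture run to an SFU Visit allowed as late as Day 62; separately, listed relative days after the dosing date are one too low

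*SAP*

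**What the plan says.** **Endpoint.** Protocol Table 3-1 and SAP Table 1-1 agree: "The secondary safety endpoint is occurrence of TEAEs from Day 1 through the SFU Visit".

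**AE capture.** Protocol 9.4.1: "Adverse events will be captured from the time of consent until the SFU Visit".

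**Timing of the SFU call.** Footnote a to the Protocol's schedule of activities, Protocol 4.1.3 and SAP 4.1.1.1 all allow 5 days either side of the nominal date, Day 57.

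**TEAE definition.** An AE counts if it starts on or after dosing and, in Protocol 9.4.1, "until 8 weeks after dosing of study medication"; in SAP 4.3.1.1, "until 8 weeks (56 days) inclusive after dosing of study medication".

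**AE classes.** SAP 4.3.1.1 has AEs "characterized as pretreatment and treatment emergent according to the intake of treatment". It provides no third class for later onsets.

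**Study periods.** SAP 4.1.1.1 closes the SFU Period at Day 57, although the same section gives the call its tolerance.

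**Relative day.** SAP 4.1.1.3 assigns 1 to the date of first dose. It then gives a rule for "an event or measurement occurring after the date of the first dose to the date of the last visit will be calculated as follows": the event date minus the date of first dose, with no 1 added. SAP Table 4-1 labels the day after dosing Day 2 and the SFU Day 57.

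**The concern.** The endpoint and the capture period end at an actual contact, while the TEAE definition ends at a fixed day. The two agree only if the call is on Day 57. After a later call, the site has recorded events that lie within the stated endpoint period but cannot be tabulated under it, and the SAP has no class to put them in.

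The TEAE tables, including those for serious and fatal TEAEs by relationship, are the summaries of the named safety endpoint, and several of them feed the registry disclosure described in SAP 6.12. With 12 to 15 participants planned, one event more or less is visible in any incidence.

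Other SAP windows are not cut at Day 57. Concomitant medication (SAP 6.6) runs to the SFU Visit, and treatment-emergent marked laboratory abnormalities (SAP 4.5.2) run to the end of the study. A drug started on Day 60 for an event that began on Day 60 would be summarized as newly concomitant, while the event itself would not be a TEAE.

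The relative-day rule is a separate matter. A reader who compares a listed event day with a visit label will be one day out for any date after dosing.

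**Working it through.** **1. The plan's own figure.** 8 weeks × 7 = 56 days. With the dosing date as Day 1, study day = (date − dosing date) + 1, so dosing + 56 days = Day 57. The TEAE limit and the nominal SFU date coincide.

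**2. The SFU tolerance.** Earliest call: 57 − 5 = Day 52. Latest call: 57 + 5 = Day 62, which is dosing + 61 days.

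**3. The gap for a call on Day c.** Days captured but outside the TEAE window = max(0, c − 57).
- c ≤ 57: 0 days.
- c = 62: 62 − 57 = 5 days (Days 58 to 62), or 5/62 = 8% of that participant's days from dosing.

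**4. The reverse case.** For a call on Day 52, AE capture ends while the TEAE window still has 57 − 52 = 5 days to run (Days 53 to 57).

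**5. An illustration that rests on an assumption.** If call dates were uniform over the 11 days from Day 52 to Day 62, 5/11 = 45% of participants would have at least one uncovered day. The mean over all participants would be (1 + 2 + 3 + 4 + 5)/11 = 15/11 = 1.36 days. The documents give no distribution of call dates. The range is 0% of participants (no call after Day 57) to 100%, and 0 to 5 days each.

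**6. Weight of one event.** If the Safety Set has 12 to 15 participants, one participant is 1/15 = 6.7% to 1/12 = 8.3% of the denominator.

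**7. Relative day.** Applying the rules in SAP 4.1.1.3 to dates around dosing:

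| Days since dosing | Visit or study day | Relative day under the SAP | With +1 from dosing onward |
|---|---|---|---|
| −1 | −1 | −1 | −1 |
| 0 | 1 | 1 | 1 |
| 1 | 2 | 1 | 2 |
| 6 | 7 | 6 | 7 |
| 56 | 57 | 56 | 57 |
| 61 | 62 | 61 | 62 |

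Two dates share the number 1, and every date after dosing is one below its visit day. Dates before dosing and the dosing date itself are numbered correctly.

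**The case against.** The strongest reply is that a fixed 8-week window is a deliberate choice, stated in both documents. The endpoint counts TEAEs, which is a defined term, and the SFU is itself described as 8 weeks after dosing. A fixed window gives every participant the same nominal period; a window tied to the call date lets its length depend on scheduling. It also does nothing for participants called before Day 57. This stands as a real cost of the change. It does not remove the conflict: the endpoint names the visit, the visit may be late, and an event with onset between Day 58 and the call has no class.

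A reader might infer that late events vanish from the report and from the registry. The documents do not support that. SAP 4.3.1.2 lists all AEs with onset date and time and includes a count of all deaths in the overview table; SAP 6.12 makes that count mandatory for disclosure. The same overview has an entry for SAEs apart from serious TEAEs, although its wording is ambiguous, and the table of discontinuations due to AEs is not restricted to TEAEs. What is lost is TEAE status and a place in the TEAE summaries.

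A reader might also take the closing of the SFU Period at Day 57 as a further loss of data. No AE summary in SAP 4.3.1.2 is by study period, so it is an inconsistency of definition with no shown effect on a table.

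On relative day, it can be said that SAP 4.1.1.3 governs listings only, that reported dates are also displayed, and that the leading plus sign in the formula may have been meant as a count of days since dosing. The first two limit the importance of the point. The third is not stated anywhere in the SAP.

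**Conclusion.** The point holds. The endpoint period, the TEAE window and the SFU tolerance are not reconciled in either document. AEs with onset from Day 58 up to a late call are collected yet left out of the named endpoint's summaries. The size is 0 to 5 days per participant and is zero for any call on or before Day 57. The calculation assumes that the 56-day limit is read by calendar date.

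Three stronger readings should be avoided:
- That nearly half of participants are affected: this needs uniform call dates, for which the documents give no basis, and it counts participants with an uncovered day, not participants with an event.
- That the relative-day rule causes events to be lost: TEAE status depends on the start date and time, and relative day is used only in listings.
- That every post-dose record is misnumbered: records later on the dosing date itself are correctly numbered 1.

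The study plans no inferential analysis, so no test or interval for the safety endpoint is at stake. Both points merit correction because they conflict with the documents' own definitions and can be settled without new data.

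**What to change.** **TEAE window**
- SAP 4.3.1.1: define a TEAE as an AE with onset on or after dosing and through the later of 56 days after dosing or the date of the SFU Visit.
- SAP 4.1.1.1: end the SFU Period at the SFU Visit.
- Protocol 9.4.1: align the definition, or record the difference in SAP 4.8, which at present lists only the medication definitions.

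**Relative day, listings only**
- SAP 4.1.1.3: use (date − date of first dose) + 1 for all dates on or after dosing, and delete the separate rule for later dates.

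**Cost.** A few sentences in a SAP amendment, plus a protocol edit or an entry in SAP 4.8. No new data are needed. A few more events may count as TEAEs. The window would vary between participants by up to 5 days with the call date, and a call before Day 57 would still end AE capture before the window closes; the report should give the call dates so that both can be seen.

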##### **4.3.1.2 Main analytical approach**

The number and percentage of participants who experience TEAEs will be summarized by MedDRA SOC, HLT, and PT. Summaries of TEAEs include, but are not limited to the following:

- Incidence of overall TEAEs (overview including number and percentage of participants with any TEAEs, serious TEAEs, discontinuations due to TEAEs, drug-related TEAEs, severe TEAEs, TEAEs leading to death, all deaths, TEAEs of Special Interest (Hy's Law), TEAEs of Special Monitoring, TEAEs of focus, ADEs, severe ADEs, and SAEs; event counts will also be included)
- Incidence of all TEAEs
- Incidence of Serious TEAEs
- Incidence of TEAEs by maximum intensity
- Incidence of TEAEs by maximum relationship
- Incidence of non-serious TEAEs above reporting threshold of 5% of study participants
- Incidence of all TEAEs by Preferred Term
- Discontinuation due to AEs
- Incidence of Serious TEAEs by Relationship
- Incidence of Fatal TEAEs by Relationship

Summary tables will contain counts of study participants, percentages of study participants in parentheses and the number of events where applicable. A participant who has multiple events in the same SOC, HLT, and PT during a given treatment will be counted only once in the participant counts for that treatment, but all events will be included.

Rozanolixizumab treatment-emergent adverse events of focus (TEAEOF) will also be analysed for the SS. TEAEOF are defined in Section 6.8. The number of and percentage of study participants who experience each category of the TEAEOF will be summarized. The following summaries will be presented by SOC, HLT and PT:

- Incidence of TEAEOF
- Incidence of Serious TEAEOF

In summaries including relationship, the following relationships will be summarized: 'Not related' and 'Related'. Participants who experience the same event multiple times will be included in the most related category for tabulations by maximum relationship. Events with missing relationship will be considered as 'Related' but recorded as missing in the listings.

In summaries including intensity, the following intensity categories will be summarized: 'Any', 'Mild', 'Moderate', and 'Severe'. Participants who experience the same event multiple times will be included in the most severe category for tabulations by maximum intensity. Events with missing intensity will be considered as 'Severe' events for summary purposes but recorded as missing in the listings.

Adverse event summaries will be ordered alphabetically by SOC and HLT within SOC, and by decreasing incidence of PT within HLT in the group column.

All AEs will be presented for the ASPS in the listings by study participant and will include the onset date/time and outcome date/time of the event, the event duration (derived), time to onset (derived), pattern of event, intensity, relationship to study drug, breast milk pump or drug delivery device, action taken, outcome and AEs that led to discontinuation.

Device deficiencies for the breast milk pump and drug delivery device will be listed for the ASPS.

### **4.3.2 Pharmacokinetics**

#### **4.3.2.1 Definition of endpoint**

The secondary PK endpoints are defined in Section 4.2.1.1 .

#### **4.3.2.2 Main analytical approach**

The main analytical approach is documented in Section 4.2.1.2 .

### **4.4 Exploratory endpoints analysis**

#### **4.4.1 Other pharmacokinetics**

The exploratory PK endpoints are described in Section 4.2.1.

### **4.5 Other Safety analysis**

In general, safety analyses will be presented on the SS unless stated otherwise.

#### 4.5.1 Vital signs

Vital signs will be measured in a semi-supine position after 5 minutes rest. The following vital signs measurements will be assessed:

- Systolic and diastolic blood pressure (BP)
- Pulse rate
- Body temperature
- Respiratory rate

The criteria for assessing if a vital sign value is abnormal is given in [Table 4–3](#).

Vital signs measurements will be summarized by visit and time point (where applicable) including observed values and changes from Baseline.

**Table 4–3: Criteria for abnormal vital signs**

Parameter	Unit	Abnormality Criteria
Systolic blood pressure	mmHg	$\leq 90$ and a decrease from Baseline of $\geq 20$ $\geq 180$ and an increase from Baseline of $\geq 20$
Diastolic blood pressure	mmHg	$\leq 50$ and a decrease from Baseline of $\geq 15$ $\geq 105$ and an increase from Baseline of $\geq 15$
Pulse rate	Beats/minute	$\leq 50$ and a decrease from Baseline of $\geq 15$ $\geq 120$ and an increase from Baseline of $\geq 15$
Body temperature	°F	$> 101$ (38.3 °C)

#### 4.5.2 Clinical laboratory evaluations

Treatment-emergent marked abnormalities (TEMA) in laboratory parameters may be analyzed. Thresholds for defining marked abnormalities for relevant laboratory parameters are available in [Appendix 6.11.1](#). MA values are considered treatment-emergent if the MA was not present before the date of first administration of the study drug and occurred on or after the date of the first administration of the study drug and before the end of the study.

Measurements below the lower limit of quantification (BLQ) will be imputed with half of the lower limit of quantification (LLOQ), and measurements above the upper limit of quantification (ALQ) will be imputed to the upper quantification limit for purposes of quantitative summaries.

Listings of clinical chemistry and hematology laboratory results will be produced for participants who had a value outside the normal ranges, including any values which are clinically significant as assessed by the investigator. These listings will include all data for each parameter for which a participant has at least one abnormal value during the study. Laboratory variables will be grouped according to the laboratory function panel (e.g., lipids, endocrine) and will be categorized as normal, high or low, if applicable, based on the reference range supplied by the analytical laboratory.

Clinical chemistry and hematology parameters will be summarized by visit for both absolute values and changes from Baseline.

Liver function laboratory results will be listed for study participants with elevated liver function results.

Urinalysis laboratory results will be listed but not summarized.

### 4.5.3 Electrocardiogram

A single 12-lead ECG will be obtained at Screening only. The following ECG parameters will be reported:

- Heart rate
- PR interval
- QT interval
- QRS interval
- QTc intervals (QT corrected for heart rate using Fridericia's formula [QTcF] and Bazett's formula [QTcB])

The criteria for assessing if an ECG parameter is abnormal is given in [Table 4-4](#). ECG parameters and any findings will be listed for the SS.

**Table 4-4: Criteria for abnormal ECG parameters**

Parameter	Unit	Abnormality Criteria
Heart rate	Beats/minute	< 50 or > 120
QT interval	ms	≥ 500
QTcF interval	ms	≥ 500
PR interval	ms	> 200
QRS interval	ms	> 100

### 4.5.4 Physical examination

Study participants with abnormalities in the physical examination will be listed including details of the abnormality and clinical significance.

### 4.5.5 Neurological evaluation

A full neurological examination will be performed for any participant who experiences severe and/or serious headache and for study participants who experience aseptic meningitis.

Study participants with abnormalities in the neurological examination will be listed including details of the abnormality and clinical significance.

### 4.5.6 Extent of exposure

Administration of treatment will be listed and will include the date of infusion, start and stop time of infusion, duration of infusion, whether the infusion was temporarily stopped or discontinued, and total volume of treatment given.

The duration of the sc infusion will be calculated as follows and will be presented in minutes:

---

Duration (minutes) = Stop time – Start time.

#### **4.5.7 Additional safety assessments**

Additional laboratory test results including alcohol urine test, urine drug screen, and serum and urine pregnancy tests will be listed for the SS.

Prior and concomitant medical procedures will be listed for the SS.

#### **4.6 Other analyses**

Not applicable.

##### **4.6.1 Subgroup analyses**

Not applicable.

#### **4.7 Interim analyses**

Not applicable.

#### **4.8 Changes to protocol-planned analyses**

The definitions of past, prior, and concomitant medications have changed from the protocol and are documented in Section 6.6.

#### **4.9 Data Monitoring Committee or other review board**

Not applicable.

### **5 SAMPLE SIZE DETERMINATION**

No formal sample size calculations have been performed as there are no statistical hypotheses being tested. It is expected that up to 20 healthy study participants will need to be screened to ensure that a minimum of 12 participants and a maximum of 15 participants provide data to assess whether there is transfer of rozanolixizumab into breast milk after a single dose and to calculate the estimated daily infant dosage and relative infant dose from breast milk. This number was selected based on feasibility and considered to be sufficient to meet the primary objective.

## **6 APPENDIX: SUPPORTING DOCUMENTATION**

### **6.1 Appendix 1: Coding dictionaries**

The medical history and adverse events (AEs) will be coded using MedDRA 27.1. Medications will be coded using the World Health Organization Drug Dictionary (WHO-DD) B3 MAR/2024. Medical procedures and device deficiencies will not be coded.

